Assessing the Relative Efficacy of Communication Modalities for Messages Promoting Flu
Shots

Study Protocol with SAP

NCT05509270

10/6/2022

Study Protocol

Scientific Background

The Centers for Disease Control (CDC) recommends a flu vaccination to everyone aged 6+ months, with rare exception; almost anyone can benefit from the vaccine, which can reduce illnesses, missed work, hospitalizations, and death. Flu shots are particularly important for patients at high risk of experiencing severe outcomes.

During the 2020-21 and 2021-22 flu seasons, the study team sent messages to Geisinger patients in the top 10% of risk for flu and complications according to an artificial intelligence algorithm. Messages that told patients they were at high risk significantly increased their likelihood of getting vaccinated.

Objectives

The present study extends previous work by testing which modality or modalities are most effective at boosting flu shot rates in patients at high risk. In previous campaigns, patients received messages via all communication modalities patients were eligible for (mailed letter, SMS text, and/or patient portal message). In this study, patients were randomized to receive high-risk messages in one or more modalities.

Design

This study is a randomized controlled trial with up to 6 study arms, depending on modality eligibility. Patients were randomized to receive high-risk messages in one or more modalities they were eligible for.

Methods

The sample included 43,225 patients. Patients were first divided into the following *modality groups* according to the modalities they were eligible for:

- A. Letter + Patient portal + SMS (29,505 patients)
- B. Letter + Patient portal (4,980 patients)
- C. Letter only (4,366 patients)
- D. Letter + SMS (4,364 patients)
- E. Patient portal + SMS (8 patients)
- F. SMS only (2 patients)

Note: there were no eligible patients who had Patient portal access only.

Then, each modality group was randomized across *study arms* the patients were eligible for:

- 1. Control (no message)
- 2. Letter only
- 3. Patient portal only
- 4. SMS only
- 5. Patient portal + SMS

6. Letter + Patient portal + SMS

For example, patients who are eligible to receive a letter and an SMS (*modality group D*) were randomized to Control (*study arm 1*), Letter only (*study arm 2*), or SMS only (*study arm 4*).

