Note: Due to power limitations, we did not test all possible combinations of modalities (e.g., we did not include a Letter + SMS study arm).

Power Analysis

Our primary analysis sample includes patients in *modality group A*, with patients eligible for all three modalities. This group includes between 4,916 and 4,919 patients per arm. This sample size allows 80% power to detect an increase in flu vaccination rates from 35% to 37.7% with alpha = .05.

Project Status

All intervention messages have been sent. Letters were sent on 9/6/22. Patient portal messages and SMS were sent on 9/8/22, to match the date when the majority of patients were expected to receive the letter (i.e., 2 days after the letters are sent). The primary outcome date was 10/4/22.

As of this writing, the study team has not yet obtained or analyzed any outcome data from the study.

Statistical Analysis Plan

Analysis Exclusion Criteria

We will remove patients from analysis who received a flu shot prior to 9/6/22, the study start date, because they could not have been influenced by our nudge messages to get a flu shot.

Planned Analyses

Primary Outcome: Flu vaccination within 4 weeks of the first message send date [Time Frame: 4 weeks after the first messages are sent in the study]

The primary analysis sample will be patients in modality group A, who are eligible for all 3 modalities and were randomized across all study arms. We will address the following four questions in this primary analysis sample:

Question 1: Are flu shot rates higher when a high-risk flu shot message is sent in any modality or combination of modalities independently compared to when no message is sent?

Hypotheses:

- 1.a. Flu shot rates will be higher in the Letter only arm than the Control arm
- 1.b. Flu shot rates will be higher in the Patient portal only arm than the Control arm
- 1.c. Flu shot rates will be higher in the SMS only arm than the Control arm
- 1.d. Flu shot rates will be higher in the Patient portal +SMS arm than the Control arm
- 1.e. Flu shot rates will be higher in the Letter + Patient portal + SMS arm than the Control arm

Analysis 1 (Confirmatory): We will run an OLS regression with a categorical independent variable coding for study arm with the Control arm coded as baseline. All 5 hypotheses above will be tested within the same regression.

Question 2: Which modality on its own most effectively increases flu shots?

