Analysis 2 (Exploratory): We will run an OLS regression with a categorical independent variable coding for study arm, including only patients randomized to be sent messages in one modality (Letter only, Patient portal only, SMS only). We will test for significant pairwise differences in flu vaccination rates between the study arms by running Tukey's HSD test.

Question 3: Are Patient portal and SMS messages better in combination than either modality alone?

Analysis 3 (Exploratory): We will run an OLS regression including patients in the Patient portal only, SMS only, and Patient portal + SMS arms, with a categorical independent variable coding for study arm. The Patient portal + SMS arm will be coded as baseline, so the individual Patient portal and SMS modalities can be compared directly against the combination of the two modalities.

Question 4: Is there value to sending a letter in addition to Patient portal and SMS messages?

Analysis 4 (Exploratory): We will run an OLS regression comparing the Patient portal + SMS study arm to the Letter + Patient portal + SMS arm, with a categorical independent variable coding for study arm.

Analyses with additional modality groups

We also will run the following **additional analyses on the primary outcome:**

Within *modality groups B* and *D* (Letter + Patient portal, Letter + SMS, respectively), we will run Analyses 1 and 2 (comparing active study arms to the control arm, and comparing active study arms to one another).

For *modality group C* (Letter only), we will run Analysis 1, comparing the letter arm to control.

Because there are so few patients in *modality groups E* (8 patients) and *F* (2 patients), we will not separately analyze data on these groups.

Finally, we will run Analyses 1 and 2 on the entire sample, with all modality groups combined.

Sensitivity Analyses and Robustness Checks

Recent work suggests that OLS regressions are appropriate in randomized experiments with binary outcome variables such as ours (Gomilla, 2021). However, as a robustness check, we will also run the regressions described above as logistic regressions instead of OLS regressions.

Other Pre-specified Outcomes

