Other Pre-specified Outcomes listed below include flu outcomes (diagnosis, complications) and COVID-19 vaccination. If there are any differences in these outcomes as a function of study arm, the mechanism would almost certainly be increased flu vaccination. Therefore, we will only run analyses on Other Pre-specified Outcomes for analyses above where there is a difference in flu vaccination.

1. High confidence flu diagnosis

Patient received a flu diagnosis via a positive polymerase chain reaction (PCR)/antigen/molecular test (yes/no) during the 2022-23 flu season (from the first message send date through April 30, 2023).

[Time Frame: Up to 8 months]

2. "Likely flu" diagnosis

Received a "high confidence flu" diagnosis (with positive PCR/antigen/molecular test) and/or "likely flu" diagnosis (as assessed via International Classification of Disease [ICD] codes or Tamiflu administration or positive PCR/antigen/molecular test) (yes/no) during the 2022-23 flu season (from the first message send date through April 30, 2023).

Note that "likely flu" is a superset of the "high confidence flu" diagnoses.

[Time Frame: Up to 8 months]

3. Flu complications

Diagnosed with flu-related complications (yes/no) from the first message send date through July 31, 2023.

[Time Frame: Up to 11 months]

4. ER visits

Number of ER visits from the first message send date through July 31, 2023.

[Time Frame: Up to 11 months]

5. Hospitalizations

Number of hospitalizations from the first message send date through July 31, 2023.

[Time Frame: Up to 11 months]

6. COVID-19 vaccination rates

Received at least one COVID-19 vaccination (yes/no) during the 2022-23 flu season (from the first message send date through April 30, 2023).

[Time Frame: Up to 8 months]

Additional Exploratory Analyses

1. Age and gender

While older patients tend to be aware of their increased vulnerability, younger patients may be more surprised to learn of their high-risk status. Additionally, our previous work suggests that males and females are differently likely to get vaccinated as a function of age, with younger females *more* likely to get vaccinated than males, and older females *less* likely to get vaccinated than older males.

We will therefore run an OLS regression including binned age (18-24, 35-44, 45-54, 65+), gender, and their interaction.

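### The whole-sample rerun of Analyses 1 and 2 names study arm as its only regressor although the available arms depend on modality group, so seven of its eight contrasts can be confounded by modality access

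*Combined protocol and SAP*

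**What the plan says.** The Design section of the protocol describes the trial thus: "This study is a randomized controlled trial with up to 6 study arms, depending on modality eligibility". Methods lists six modality groups: A (29,505 patients), B (4,980), C (4,366), D (4,364), E (8) and F (2). Each group was randomized over the arms open to it. Group D, for example, had only Control, Letter only and SMS only.

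In the SAP (Planned Analyses), Analysis 1 reads: "We will run an OLS regression with a categorical independent variable coding for study arm with the Control arm coded as baseline". Analysis 2 is an OLS regression on study arm "including only patients randomized to be sent messages in one modality", followed by Tukey's HSD. Neither names another covariate.

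The confirmatory analysis uses group A only. Under Analyses with additional modality groups, B, C and D are first analysed separately. The section then ends: "Finally, we will run Analyses 1 and 2 on the entire sample, with all modality groups combined". No modality-group term, stratification or weighting is given for that run. The logistic robustness check refits the same regressions.

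Other Pre-specified Outcomes adds a dependency: "we will only run analyses on Other Pre-specified Outcomes for analyses above where there is a difference in flu vaccination".

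**The concern.** Randomization protects comparisons within a modality group. Across groups, a patient's chance of landing in a given arm depends on which modalities the patient could receive. Groups B, C and D supply Control patients to the pooled run but none to the combination arms. Group C supplies Control and Letter patients only. A pooled regression on arm alone therefore compares populations with different modality access, and any difference in their vaccination rates enters the estimated message effect.

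Two things are at stake. The pooled run could report that a modality works, or works better than another, when the difference reflects who has portal or SMS access. It could then contradict the valid within-group results. Also, a spurious pooled difference could meet the plan's condition for analysing flu diagnosis, complications, ER visits, hospitalizations and COVID-19 vaccination. Those analyses would be confounded in the same way if run on the pooled sample with arm alone.

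**Working it through.** **The plan's own figure.** With 4,916 per arm, 35% vs 37.7% and two-sided alpha .05, the pooled rate is 0.3635. The null SE is √(2 × 0.3635 × 0.6365 / 4,916) = 0.00970, and the SE under the alternative is also 0.00970. Power = Φ((0.027 − 1.96 × 0.00970) / 0.00970) = Φ(0.82) = 79.5%, which agrees with the stated 80%. The group sizes sum to 43,225, and 29,505 / 6 = 4,917.5 fits the statement "This group includes between 4,916 and 4,919 patients per arm". Allocation in group A is therefore equal.

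**Arm composition.** I assume equal allocation in the other groups too; the documents do not state it. Per-arm sizes are A 29,505/6 = 4,917.5; B 4,980/3 = 1,660; C 4,366/2 = 2,183; D 4,364/3 = 1,454.7; E 8/4 = 2; F 2/2 = 1. These are before the prior-shot exclusion.

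| Pooled arm | n | A | B | C | D |
|---|---|---|---|---|---|
| Control | 10,218 | 48.1% | 16.2% | 21.4% | 14.2% |
| Letter only | 10,215 | 48.1% | 16.2% | 21.4% | 14.2% |
| Patient portal only | 6,580 | 74.7% | 25.2% | 0 | 0 |
| SMS only | 6,375 | 77.1% | 0 | 0 | 22.8% |
| Portal + SMS | 4,920 | 99.96% | 0 | 0 | 0 |
| Letter + Portal + SMS | 4,918 | 100% | 0 | 0 | 0 |

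Groups E and F make up the small remainders. Four of the five Analysis 1 contrasts and all three Analysis 2 pairs compare different mixes.

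**Bias under no message effect.** Assume group A at 35% (the base rate in Power Analysis) and every other group lower by a common gap d. Then bias = d × (share of A in the arm − share of A in Control). At d = 5 points:

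- Combination arms: 5 × (1.000 − 0.481) = 2.6 points
- Patient portal: 5 × (0.747 − 0.481) = 1.3 points
- SMS: 5 × (0.771 − 0.481) = 1.5 points
- Letter: 5 × (0.481 − 0.481) = 0.0 points

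The rejection rate at unadjusted two-sided .05 is Φ(z − 1.96) + Φ(−z − 1.96), with z = bias / SE. For Letter + Portal + SMS at d = 5, z = 2.594 / 0.818 = 3.17, giving 89%.

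| Contrast vs Control | Bias, d = 0 / 2 / 5 points | False-positive rate |
|---|---|---|
| Each combination arm | 0 / 1.0 / 2.6 | 5 / 24 / 89% |
| Patient portal only | 0 / 0.5 / 1.3 | 5 / 11 / 43% |
| SMS only | 0 / 0.6 / 1.5 | 5 / 12 / 49% |
| Letter only | 0 / 0.0 / 0.0 | 5 / 5 / 5% |

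If the other groups are 5 points higher instead, the signs reverse.

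**Analysis 2.** Letter vs portal and Letter vs SMS carry the same biases as portal and SMS vs Control, because Letter and Control have the same mix. In simulation, the chance of at least one false Tukey difference is about 5%, 11–12% and 48% at gaps of 0, 2 and 5 points. Portal vs SMS is off by only 0.1 point if B and D are both 5 points lower. If only one of them is, it is off by 0.252 × 5 = 1.3 points (B) or 0.228 × 5 = 1.1 points (D).

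**Check of the remedy.** When each contrast uses only groups holding both arms, with group indicators, the bias is 0.0. Simulated per-test error against Control is 4.9–5.2% at the 5-point gap. One additive arm-plus-group model is also unbiased under no message effect, but it assumes that arm effects are constant across groups. If Letter adds 5 points in B–D only and nothing else works, the additive model returns +0.53 (portal), +0.57 (SMS) and +0.93 points (each combination arm). The restricted contrasts return 0.0.

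**The case against.** The stakes are limited. The pooled run comes last among the additional analyses. No numbered hypothesis and no power statement rests on it, and valid within-group estimates will stand beside it, so a discordant result would be visible. The plan is silent on covariates rather than excluding them. The size of the bias rests on assumed gaps: at 1 point the combination arms are off by only 0.5 point, with about 10% rejection, and at zero gap there is no bias. The plan does not say on which sample or with which model the other outcomes would be analysed. Finally, group indicators alone would remove the baseline confounding with a smaller loss of precision, and the scenario against the additive model was chosen for illustration; with a 2-point Letter effect in B–D its errors fall to +0.21, +0.23 and +0.37 points.

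Most of this stands as a limit on weight. It does not remove the point. An analyst who follows the text would fit arm alone, and the imbalance in mix for the combination arms follows from eligibility, whatever the allocation ratios in B–D. The additive model is acceptable if its assumption is stated.

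**Conclusion.** The concern holds, as a flaw that should be fixed in a supplementary analysis. The structural point is firm: seven of the eight pooled contrasts compare arms with different modality-group mixes. Its size is conditional, because the documents give no vaccination rates by group. At an assumed 5-point gap, the spurious 2.6 points for the combination arms nearly equal the 2.7-point difference (35% to 37.7%) that the trial was sized to detect.

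Letter vs Control is essentially unbiased, provided the Control:Letter ratio is the same in groups A to D; the documents show equal allocation only for A. The confirmatory group A analysis and the separate analyses of B, C and D are not affected.

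**What to change.** For the whole-sample OLS and logistic runs, specify that each contrast is estimated only from modality groups randomized to both arms, with modality-group indicators:

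- Letter vs Control: A, B, C, D
- Portal vs Control: A, B (plus E)
- SMS vs Control: A, D (plus E and F)
- Letter vs portal: A, B
- Letter vs SMS: A, D
- Portal vs SMS: A (plus E)

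State that the combination arms vs Control rest essentially on group A, so the pooled run adds nothing for them. The three Analysis 2 pairs then use different samples, so replace the single Tukey test in this run with Holm across the three pairs. In the logistic runs omit E and F (10 patients), because indicators for so few patients can cause separation. If one additive arm-plus-group model is preferred, state that it assumes constant arm effects across groups. Apply the same specification to any other outcome analysed on the pooled sample.

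The cost is a short SAP paragraph and separate contrast models; modality group is already recorded. At a 35% rate, SE = √(0.2275 / Σ n₁n₂/(n₁+n₂)), summed over the groups used. For portal vs Control the sum is 2,458.75 + 830 + 1 = 3,289.75.

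| Contrast | SE, arm only (points) | SE, restricted (points) |
|---|---|---|
| Letter vs Control | 0.67 | 0.67 |
| Portal vs Control | 0.75 | 0.83 |
| SMS vs Control | 0.76 | 0.845 |
| Each combination arm vs Control | 0.83 | 0.96 |
| Portal vs SMS | 0.84 | 0.96 |

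Portal and SMS vs Control remain more precise than in group A alone (0.96). The additive model would give 0.79 (portal), 0.80 (SMS) and 0.88 (combination arms).

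Project Status says that no outcome data had been obtained when the document, dated 10/6/2022, was written. The documents cannot show whether that still holds, so date the change and state whether outcome data had been seen.

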We will also test for an interaction between age, gender and study arm, as people of different ages and genders may be differentially receptive to different modalities.

2. Timing of shot

We will run regression models to test whether intervention messages influenced the timing (time elapsed since the beginning of the intervention, September 6, 2022) of flu shots.

3. Risk level

As in our studies in the 2020-21 and 2021-22 flu seasons, patients who were in the top 3% of risk were told they were in the top 3% of risk, while those in the next 7% (i.e., the top 4-10% of risk) were told they were in the top 10% of risk. We will test whether flu vaccination rates differ across risk level (top 3%, top 10%) and whether risk level interacts with study arm among patients in *modality group A* who have access to all 3 modalities.

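### The age bins in the exploratory age-by-gender regression leave out ages 25-34 and 55-64

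*Combined protocol and SAP*

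**What the plan says.** The SAP, Additional Exploratory Analyses, item 1 (Age and gender), plans an OLS regression on "binned age (18-24, 35-44, 45-54, 65+), gender, and their interaction". The same item continues: "We will also test for an interaction between age, gender and study arm". It gives no age coding for that second model and does not name the sample for either model.

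The reason given is a contrast across age: "While older patients tend to be aware of their increased vulnerability, younger patients may be more surprised to learn of their high-risk status". The item adds that, in the team's previous work, the gender difference in vaccination changed direction between younger and older patients.

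On who is analysed, Methods says "The sample included 43,225 patients" and states no age restriction. Analysis Exclusion Criteria has one rule: "We will remove patients from analysis who received a flu shot prior to 9/6/22, the study start date". Project Status says that, at the time of writing, "the study team has not yet obtained or analyzed any outcome data from the study".

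**The concern.** A categorical age variable in a regression should give every analysed patient a level. Here two ten-year bands have none. The list is running text, so neither a broken table nor a redaction explains the gap.

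An analyst who follows the text literally codes these patients as missing, and the software drops them. The model then says nothing about 25-34 or 55-64 and does not describe the full sample. This touches the purpose of the analysis. If the gender difference reverses somewhere along the age scale, locating the reversal needs the whole scale, and 55-64 is the step between the last two listed bins.

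An analyst who repairs the list must choose the bins. If that happens after outcomes are seen, the choice is no longer pre-specified.

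**Working it through.** **Plan's own figure.** The document gives no number for this analysis. Its only design calculation is the power statement in Power Analysis, which does not involve age. It reproduces. With 4,916 per arm ("This group includes between 4,916 and 4,919 patients per arm"), rates of 35% and 37.7%, and two-sided alpha of .05:

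- SE = sqrt[(0.35 × 0.65 + 0.377 × 0.623)/4,916] = 0.0097
- 0.027/0.0097 = 2.78, and 2.78 − 1.96 = 0.82
- power = 79.5%, against the stated 80%

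This figure is unaffected by the bins.

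**Coverage.** The document states no minimum age, so 18 is inferred from the first bin. Checking each whole year from 18 upward against the four bins leaves 20 years uncovered: 25 to 34 and 55 to 64.

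**Can the intended list be inferred?** At least three exhaustive lists resemble the printed one. With b bins, two gender categories and six arms, the age-by-gender interaction has b − 1 df, the three-way interaction has (b − 1) × 1 × 5 df, and there are 12b cells. The last column is 29,505/(12b), using group A before the prior-vaccination exclusion.

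| Bins | b | Age × gender df | Three-way df | Cells | Mean patients per cell |
|---|---|---|---|---|---|
| 18-34, 35-44, 45-64, 65+ | 4 | 3 | 15 | 48 | 615 |
| 18-34, 35-44, 45-54, 55-64, 65+ | 5 | 4 | 20 | 60 | 492 |
| 18-24, 25-34, 35-44, 45-54, 55-64, 65+ | 6 | 5 | 25 | 72 | 410 |

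These are different tests. Changing only 18-24 to 18-34 still leaves 55-64 uncovered, so correcting one bin is not enough. The six-bin list is the only one of the three that keeps every printed endpoint.

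**Effect on the listed bins.** A model with age bin, gender and their interaction, and nothing else, fits each cell by its own mean. Leaving out other cells therefore does not change the coefficients of the listed bins. Standard errors move slightly, because the residual variance is pooled over fewer patients. A simulation with n = 29,505 and an assumed age distribution (its values are not estimates for this trial) compared three fits:

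- The 65+ versus 18-24 coefficient was 0.1834 whether the two decades had their own bins or were omitted, with standard errors of 0.0244 and 0.0245.
- If the unbinned patients fell into the 18-24 reference level through careless dummy coding, that contrast became 0.0991.
- The 45-54 minus 35-44 contrast was 0.0410 in all three fits.

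**Number affected.** The document gives no age distribution. Taking 5% to 40% in the two gaps as an assumption:

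- Group A: 0.05 × 29,505 = 1,475 to 0.40 × 29,505 = 11,802.
- Full sample: 0.05 × 43,225 = 2,161 to 0.40 × 43,225 = 17,290.

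Both bases are counted before the prior-vaccination exclusion.

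**The case against.** The strongest reply is that this is a slip in a list, in an analysis labelled exploratory. All four printed bins fit unchanged into the six-bin scheme, so the intent is fairly clear and the analyst's freedom is narrow. Age is also a baseline variable that the intervention cannot alter. Dropping two decades would add an exclusion that the SAP does not contain, so an incomplete list is at least as natural a reading as a deliberate omission. The second model belongs to the same item and presumably uses the same bins. The 5-40% range has no support in the document, the reference-level error is hypothetical, and the choice of analysis sample is a separate matter.

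Much of this stands. A slip is likely, six bins is the most natural repair, and the illustrative range carries no weight as evidence. The unchanged coefficients also depend on the model having no further terms, which the text does not state. What remains is that the printed rule, followed as written, loses part of the sample, and that the document does not settle which repair was meant. A reader comparing the published analysis with the SAP could not tell whether the added bins were planned.

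**Conclusion.** The concern holds. The printed bins omit exactly 25-34 and 55-64, and no other part of the document closes the gap. The consequence is limited to incomplete coverage in one exploratory analysis and, if the same coding carries over, in its interaction with study arm. Estimates for the listed bins are unchanged provided the model holds only age, gender and their interaction and the unbinned patients are not absorbed into another level. Confirmatory Analysis 1, Analyses 2-4 and the power statement are unaffected. How many patients would be lost cannot be derived from the document; the counts above show only what assumed shares would mean. The list should be corrected, but the point does not threaten the trial's main conclusions.

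**What to change.** Before outcome data are accessed, replace the list with contiguous, exhaustive bins: for example 18-24, 25-34, 35-44, 45-54, 55-64 and 65+, or 18-34, 35-44, 45-54, 55-64 and 65+ if the youngest cells are thin. State that the same coding applies to the interaction of age, gender and study arm.

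Also name the analysis sample. Item 3 (Risk level) specifies modality group A for its interaction, and Analyses with additional modality groups says "we will run Analyses 1 and 2 on the entire sample, with all modality groups combined", but the age and gender item specifies neither.

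If outcome data have already been accessed, make the same change and report the added bins as chosen after the plan.

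The cost is one or two lines of SAP text and no new data. Going from four bins to six raises the age-by-gender interaction from 3 to 5 df and the three-way interaction from 15 to 25 df. In group A that means 72 cells averaging about 410 patients, although actual cells will be uneven.
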